6.3.2 Disease Progression

Disease progression will be documented in an eCRF intended to capture such information. Signs and symptoms related to disease progression should be reported in the appropriate eCRF as an AE or as a SAE if applicable. Verbatim terms such as "disease progression," "progressive disease," etc. should not be reported as AEs or SAEs unless the Investigator considers the progression to be atypical, accelerated, or caused by the investigational products. Similarly, death occurring as a result of disease progression should be reported on the eCRF intended to capture death information and should not be reported as an SAE.

6.3.3 Serious AEs or Serious SARs

Apexigen (or designee) must be notified of the occurrence of any SAE/SSAR within 24 hours of Investigator's knowledge of the event. The SAE/SSAR will be reported by completing and submitting the SAE/SSAR report form by:

Email: [contact]

If only limited information is initially available, follow-up reports are required and must be submitted in a timely fashion as additional information becomes available. The immediate and follow-up reports should identify subjects by unique code numbers assigned to the trial subjects rather than by the subjects' names, personal identification numbers, and/or addresses.

The Investigator should also comply with the applicable regulatory requirements related to the reporting of SAEs/SSARs to the regulatory authorities and the Institutional Review Board

(IRB)/Independent Ethics Committee (IEC). The sponsor may request additional source documentation pertaining to the SAE/SSAR from the investigational site. If a subject is permanently withdrawn from the study due to an SAE/SSAR, this information must be included in the initial or follow up SAE/SSAR report in the eCRF.

The sponsor is responsible for notifying the appropriate health authorities of serious and unexpected SAR (SUSAR) through expedited IND safety reports (ISR) in accordance with applicable laws and regulations.

6.3.4 Handling of Expedited Safety Reports

Apexigen (or designee) will notify Investigators of all ISRs. Upon receiving an ISR from Apexigen (or designee), the Investigator must review and retain the ISR with the Investigator's Brochure. Where required by local regulations or when there is a central IRB/IEC for the study, Apexigen (or designee) will submit the ISR to the appropriate IRB/IEC. The Investigator and IRB/IEC will determine if the informed consent requires revision. The Investigator should also comply with the IRB/IEC procedures for reporting any other safety information.

6.3.5 Non-serious AEs

The collection of AE information begins after subject's written consent to participate in the study: AEs that occur after consent, but prior to the first dose should be recorded as Medical History. If an ongoing AE changes in its intensity or in its perceived relationship to investigational product, a new AE entry for the event should be completed. AEs should be followed to resolution, stabilization, a minimum of 30 days after the discontinuation of the investigational product, or reported as SAEs if they become serious.

6.3.6 Laboratory Test Abnormalities

Laboratory test values captured as part of the study should be recorded on the appropriate pages of the eCRF. Laboratory abnormalities that meet any of the following criteria will also be captured on the AE or SAE reporting eCRF page as appropriate:

- Require the subject to have any of the investigational products discontinued, delayed, or interrupted
- Require the subject to receive specific corrective therapy
- Are clinically significant
- Meet the definition of an SAE/SSAR.

6.4 Pregnancy

Subjects will be instructed to notify the Investigator as soon as possible after becoming pregnant or learning of the pregnancy of a partner. If a subject or partner of a subject becomes pregnant during treatment or up to 120 days following the last study drug administration, the Investigator will notify Apexigen (or designee) within 24 hours of learning of the pregnancy.

If the subject becomes pregnant while receiving investigational product, the investigational product will be permanently discontinued. Exceptions to the investigational product discontinuation may be considered for life-threatening conditions only after consultation with the sponsor. The Investigator will discuss the risks and concerns of investigational drug exposure to a developing fetus and counsel the subject and/or pregnant partner (or ensure that such counseling is provided).

Pregnancies will be followed through the outcome of the pregnancy. Newborns should be followed for a minimum of 8 weeks.

The Investigator will complete a Pregnancy Surveillance Form and report the information regarding the pregnancy, outcome, and status of the newborn, as appropriate.

Protocol-required procedures for study discontinuation and follow-up must be performed on the subject unless contraindicated by pregnancy. Other appropriate pregnancy follow-up procedures should be considered if indicated.

7. Statistics

7.1 Sample Size Determination

This is a Phase 1b-2, study. The sample size for the Phase 1b dose-escalation cannot be precisely estimated but depends upon the observed toxicities. Cohorts of 3 to 6 subjects will be treated at each DL during dose escalation portion of the study. It is anticipated that approximately 18 subjects will be treated in this portion of the study depending on the actual rate of DLTs.

Sample size for Phase 2 is calculated using the Simon optimal 2-stage design [32]:

- **Cohort 1 (inNSCLC):** Assuming a false positive rate (α) of 0.1 (one-sided), a false negative rate (β) of 0.1, a response probability of poor drug (P0) of 22% and a response probability of good drug (P1) of 40%, first stage sample size (n1) is 24 and the maximum sample size (n) is 45 response evaluable subjects. In the first stage, if there are 5 or less responses in 24 subjects, the enrollment in this cohort will be stopped. Otherwise, if 6 or more responses are observed, 21 additional subjects will be accrued in Stage 2 for total of 45. Enrollment may continue into Stage 2 while the planned number of subjects for Stage 1 are followed for efficacy. By the end of Stage 2, if 13 or less responses are observed in 45 subjects, then no further investigation is warranted. If 14 or more responses are observed, the null hypothesis will be rejected and true RR is 40%.

The sample size of 45 subjects, provides 97% power to statistically test the null hypothesis of historical 6-month PFS rate (PFSR) of 60% (estimated for pembrolizumab in Keynote-024 [33]) versus the alternative hypothesis of 6-month PFSR rate of 80%. This calculation assumes exponential PFS, 1-sided 5% type I error rate, enrollment of subjects for 8 months with 6 months of follow-up prior to conducting the final analysis.

- Cohort 2 (PD1-MM): Assuming α of 0.1 (one-sided), β of 0.1, P0 5% and P1 of 20%, n1 is 12 and n is 37 response evaluable subjects. In the first stage, if there are no responses in 12 subjects, the enrollment in this cohort will be stopped. Otherwise, if 1 or more responses are observed, 25 additional subjects will be accrued in Stage 2 for total of 37. Enrollment may continue into Stage 2 while the planned number of subjects for Stage 1 are followed for efficacy. By the end of Stage 2, if 3 or less responses are observed in 37 subjects, then no further investigation is warranted. If 4 or more responses are observed, the null hypothesis will be rejected and true RR is 20%.

The sample size of 37 subjects, provides 92% power to statistically test the null hypothesis of historical 6-month PFSR of 19% (estimated for ipilimumab following nivolumab or pembrolizumab [34]) versus the alternative hypothesis of 6-month PFSR rate of 38%. This calculation assumes exponential PFS, 1-sided 5% type I error rate, enrollment of subjects for 8 months with 6 months of follow-up prior to conducting the final analysis.

- Cohort 3 (PD1-NSCLC) Group A and Group B: Assuming α of 0.1 (one-sided), β of 0.1, P0 5% and P1 of 20%, n1 is 12 and n is 37 response evaluable subjects in each group. In the first stage, if there are no responses in 12 subjects, the enrollment in that group will be stopped. Otherwise, if 1 or more responses are observed, 25 additional subjects will be accrued in Stage 2 for total of 37 per group. Enrollment may continue into Stage 2 while the planned number of subjects for Stage 1 are followed for efficacy. By the end of Stage 2, if 3 or less responses are observed in 37 subjects, then no further investigation is warranted. If 4 or more responses are observed, the null hypothesis will be rejected and true RR is 20%.

The sample size of 37 subjects/group, provides 94% power to statistically test the null hypothesis of historical 6-month PFSR of 22% (estimated for chemotherapy regimens [35, 36]) versus the alternative hypothesis of 6-month PFSR rate of 43%. This calculation assumes exponential PFS, 1-sided 5% type I error rate, enrollment of subjects for 8 months with 6 months of follow-up prior to conducting the final analysis.

Accrual is expected to be completed within 24 months from study start.

7.2 Populations for Analyses

All subjects receiving both investigational products will be included in the safety population.

Subjects evaluable for DLT are defined as those who meet study eligibility criteria, receive the entire planned dose of APX005M and nivolumab and have follow-up for at least 21 days (i.e., subject does not come off study for reasons other than toxicity).

Subjects evaluable for efficacy (tumor response) are defined as those who meet study eligibility criteria and have at least one on treatment (post baseline) tumor assessment.

Subjects evaluable for PK are defined as those who have adequate APX005M serum concentration-versus-time data to allow proper estimation of PK parameters.

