2.2 Study Design and Duration

This is a Phase 1b-2 study. The study will include 2 parts ([Table 1](#)).

- Phase 1b dose-escalation of APX005M:
 - Up to 4 dose levels of APX005M administered IV every 21 days
 - In combination with nivolumab 360 mg IV every 21 days
 - Subjects with inNSCLC or PD1-MM
- Phase 2 dose-expansion (Simon optimal 2-stage design):
 - The RP2D dose of APX005M administered IV every 21 days in combination with nivolumab 360 mg IV
 - 3 cohorts
 - Cohort 1: Subjects with inNSCLC
 - Cohort 2: Subjects with PD1-MM
 - Cohort 3: Subjects with PD1-NSCLC
 - Group A: Subjects with PD1-NSCLC with best response of progressive disease or with stable disease < 16 weeks while on

- previous PD-1/PD-L1 containing regimen
- Group B: Subjects with PD1-NSCLC with tumor response or with stable disease \geq 16 weeks while on previous PD-1/PD-L1 containing regimen

Table 1: Planned Number of Subjects in Study APX005M-002

Study Phase		APX005M		Nivolumab		
Phase 1b	Dose Level	mg/kg		mg	N	
Dose-escalation						
	DL 1	0.03	q 21 days	360	q 21 days	3
	DL 2	0.1	q 21 days	360	q 21 days	3
	DL2a	0.2	q 21 days	360	q 21 days	3 to 6
	DL 3	0.3	q 21 days	360	q 21 days	3 to 6
					Subtotal	~ 18

Study Phase		APX005M		Nivolumab		
Phase 2	Stage	mg/kg		mg	N	
Dose-expansion						
Cohort 1 inNSCLC	Stage 1	RP2D	q 21 days	360	q 21 days	24
	Stage 2	RP2D	q 21 days	360	q 21 days	21
Cohort 2 PD1-MM	Stage 1	RP2D	q 21 days	360	q 21 days	12
	Stage 2	RP2D	q 21 days	360	q 21 days	25
Cohort 3 PD1-NSCLC Group A	Stage 1	RP2D	q 21 days	360	q 21 days	12
	Stage 2	RP2D	q 21 days	360	q 21 days	25
Cohort 3 PD1-NSCLC Group B	Stage 1	RP2D	q 21 days	360	q 21 days	12
	Stage 2	RP2D	q 21 days	360	q 21 days	25
					Total	~ 174

Phase 1b dose-escalation:

Subjects with inNSCLC or PD1-MM who meet all of the general eligibility criteria will be enrolled in the dose-escalation portion of the study.

There will be a maximum of 3 escalation dose levels (DL) and 1 de-escalation dose level in this study. The doses of APX005M and minimum number of subjects to be enrolled in each dose level are presented in [Table 2](#). It is expected that up to 18 DLT-evaluable subjects (see definition in [Section 7.2](#)) will be enrolled in the dose-escalation portion of the study over a 6-month period. All subjects that are not DLT-evaluable will be replaced for the purpose of establishing MTD.

Table 2: APX005M Dose Levels

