Escalation Dose Level	DL1	DL2		DL3
De-escalation Dose Level			DL2a	
APX005M mg/kg body weight	0.03	0.1	0.2	0.3
Minimum number of DLT evaluable subjects	3	3	3	3

Abbreviations: DL = dose level; DLT = dose-limiting toxicity.

The DLT observation period for dose escalation is the 21 days following the first administration of APX005M and nivolumab (first 3-week cycle). Safety and tolerability of the APX005M and nivolumab combination will be monitored by representatives from Apexigen and the Investigators on a regular basis and prior to each dose escalation.

Dose escalation will continue if 0 out of 3 evaluable subjects experience a DLT during the DLT observation period (i.e., <33% DLT-evaluable subjects in that cohort have a DLT). If 1 DLT-evaluable subject in any DL cohort experiences a DLT, that cohort will be expanded to include additional 3 DLT-evaluable subjects (i.e. a total of 6 evaluable subjects). Dose escalation will continue if 1 out of 6 evaluable subjects experience a DLT during the DLT observation period (i.e., <33% DLT-evaluable subjects in that cohort have a DLT). Decision to open a new DL cohort will be based on the totality of the data available at that time.

The MTD is the maximum dose of APX005M combined with 360 mg of nivolumab for which <33% of DLT-evaluable subjects experience a DLT.

If the DLT rate in DL 3 exceeds 33%, or 2 or more subjects in DL 2 experience a Grade 2 infusion reaction/cytokine release syndrome, or at the discretion of the sponsor, the intermediate lower DL 2a will be evaluated (de-escalation). Up to 6 subjects can be enrolled in any of dose levels below the MTD or highest DL tested, should sponsor decide to discontinue dose escalation prior to reaching the MTD.

The RP2D will be based on the overall safety and tolerability of the combination of APX005M and nivolumab.

Phase 2 dose-expansion:

After identification of the RP2D of APX005M in combination with nivolumab 360 mg IV every 21 days, study will continue with 3 cohorts.

- Cohort 1: inNSCLC
- Cohort 2: PD1-MM
- Cohort 3: PD1-NSCLC
 - Group A
 - Group B

[figure not shown]
Each cohort and group of the Phase 2 dose-expansion portion of the study will follow a Simon optimal 2-stage design. Subjects treated at the RP2D in the dose-escalation portion will be included in Stage 1 of the relevant cohort. Additional subjects will be enrolled for a total of 24

subjects in Cohort 1 and 12 subjects in each of Cohort 2, Cohort 3 Group A and Cohort 3 Group B.

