 - **Grade 1-2:** symptomatic treatment (e.g. antihistamines, topical steroids). For persistent ($>1-2$ weeks) or recurrent symptoms consider skin biopsy and treatment delay.
 - **Grade 3-4:** consider skin biopsy and consult dermatologist. Treat with IV corticosteroids followed by oral corticosteroids until symptoms improve to Grade 1 or less.
- **Infusion Reaction/Cytokine Release Syndrome**

Precautions should be observed during the administration of APX005M and nivolumab. Emergency agents including oxygen, oral and endotracheal airways, intubation equipment epinephrine, antihistamines, and corticosteroids should be available and used if required at the Investigator's discretion.

Subjects should be instructed that symptoms associated with cytokine release syndrome/infusion reaction can occur within 48 hours following the administration of the APX005M or nivolumab, and if such symptoms develop while they are at home, they should contact the Investigator and/or seek emergency medical care if appropriate.

- **Grade 2:** stop infusion and treat symptoms following guidance in [Table 3](#). If symptoms resolve within two hours, the infusion may be restarted at 50% of the original infusion rate (e.g., from 100 mL/hr to 50 mL/hr).
- **Grade 3-4:** stop infusion and treat symptoms following guidance in [Table 3](#).

Table 3: Guidance for Management of Cytokine Release/Infusion Reaction Symptoms

Suspected Cytokine Release/Infusion-related Toxicity		Recommended Treatment

 Mild toxicity requiring symptomatic treatment only (e.g., fever, nausea, fatigue, headache, myalgia, malaise) 		
 Vigilant supportive care Maintain adequate hydration Antipyretics, non-steroidal anti-inflammatory drugs, antihistaminics, anti-emetics, analgesics as needed In case of mild symptoms persisting for > 48 hours assess for infections; empiric treatment of concurrent bacterial infections

 Symptoms or clinical findings requiring and responding to moderate intervention, such as: 
 O₂ requirement < 40% Hypotension responsive to fluids ± low dose of one vasopressor (e.g., < 50 mg/min phenylephrine) CTCAE Grade 2 organ toxicity 	
 No extensive co-morbidities 	
 All of the above Monitor cardiac and other organ functions closely

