3.5 Dose Limiting Toxicity

All toxicity will be graded according to the NCI-CTCAE version 4.03. DLT will be defined as any of the following events attributed to APX005M and nivolumab combination (e.g., AEs that are not clearly attributable to extraneous causes), and occurring during the first 21-day following the administration of APX005M and nivolumab (the first 3-week cycle):

- Grade 4 hematologic toxicity lasting ≥ 7 days (except asymptomatic lymphopenia)
- Grade 3 or 4 neutropenia with a single temperature of $>38.3^{\circ}\text{C}$ (101°F) or a sustained temperature of $\geq 38^{\circ}\text{C}$ (100.4°F) for more than one hour
- Grade 4 thrombocytopenia (platelet count $<25,000$ cells/ mm^3) or Grade ≥ 3 thrombocytopenia with signs or symptoms of bleeding or requiring platelet transfusion
- Grade 4 non-hematologic toxicity (not laboratory)
- Grade 3 non-hematologic toxicity (not laboratory) lasting >3 days despite optimal supportive care
- Any Grade ≥ 3 non-hematologic laboratory value if:
 - Medical intervention is required to treat the subject, or
 - The abnormality leads to hospitalization, or
 - The abnormality persists for >1 week
- Failure to recover from a treatment-related AE to baseline or \leq Grade 1 within 12 weeks of last dose of investigational product (except Grade 2 alopecia and Grade 2 fatigue)
- Grade 5 toxicity.

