3.7 Dose Modifications

Suspected adverse reactions (SAR) (for definition see [Section 6.1.2](#)) associated with APX005M and nivolumab exposure may represent an immunologic etiology. These AEs may occur shortly after the administration of investigational products or several months after the last dose of investigational product. Management of suspected adverse drug reactions may require treatment hold, dose reduction of APX005M, or discontinuation of one of both investigational products as per [Table 4](#). If a subject experiences several toxicities, the recommended dose modification should be based on the highest grade toxicity.

See [Section 3.4.1.2](#) for supportive care guidelines, including use of corticosteroids.

Table 4: Dose Modification Guidelines for Suspected Adverse Reactions

Toxicity	Grade	APX005M	Nivolumab
Neutropenia (± febrile)	3-4	Hold	Hold
Thrombocytopenia	3	Hold. Dose reduction if > 7 days	Hold
	4	Hold. Dose reduction	Hold. Discontinue if > 7 days
	3-4 with bleeding	Discontinue	Discontinue
Diarrhea/colitis	2	1 st occurrence: hold 2 nd occurrence: dose reduction	Hold
	3	1 st occurrence: dose reduction 2 nd occurrence: discontinue	Discontinue
	4	Discontinue	Discontinue
Uveitis, eye pain or blurred vision that does not improve to Grade 1 before next cycle	2-4	Hold	Discontinue
Increased bilirubin	2	Hold	Hold
	3-4	Discontinue	Discontinue
Increased AST, ALT	2	Hold	Hold
	3	Hold. Dose reduction For subjects with liver metastasis reduce dose only if Grade 3 > 72 hours	Discontinue
	4	Discontinue	Discontinue
Endocrinopathies	2	Hold	Hold
	3-4	1 st occurrence: Hold. Institute endocrine replacement therapy 2 nd occurrence: discontinue after consultation with Medical Monitor	1 st occurrence: Hold. Institute endocrine replacement therapy* 2 nd occurrence: discontinue after consultation with Medical Monitor
Nivolumab infusion reaction	2	Administer additional premedication. Increase infusion time to 90 min	1 st occurrence: continue 2 nd occurrence: discontinue
	3	Hold for 1 cycle. Continue single agent at following cycle	Discontinue
	4	Discontinue	Discontinue

Toxicity	Grade	APX005M	Nivolumab
APX005M infusion reaction/cytokine release syndrome	3	Hold. Dose reduction	Hold
	4	Discontinue	Discontinue
Pneumonitis	2	1st occurrence: hold 2nd occurrence: discontinue	1st occurrence: hold 2nd occurrence or if > 14 days: discontinue
	3-4	Discontinue	Discontinue
Creatinine elevation	2	Hold	Hold. Discontinue if > 7 days
	3	Hold	Hold. Discontinue if > 7 days

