3.3 DLT-Evaluable Population

The DLT-evaluable population is defined as all participants of Phase 1b who met all eligibility criteria, received the entire planned dose of APX005M and nivolumab during the DLT observation period and have completed a follow-up period after administration of study drug for at least 21 days (one full treatment cycle; i.e., participant does not come off study for reasons other than toxicity).

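### The DLT-evaluable definition drops a Phase 1b subject whose first dose is cut short by a DLT, so that DLT leaves the DLT rate and the MTD

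*Protocol*

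**What the plan says.** Protocol section 7.2 sets three joint conditions: "Subjects evaluable for DLT are defined as those who meet study eligibility criteria, receive the entire planned dose of APX005M and nivolumab", and at least 21 days of follow-up. A parenthesis after the follow-up condition explains that the subject must not leave the study for a reason other than toxicity. SAP section 3.3 has the same structure. Its dose condition, "received the entire planned dose of APX005M and nivolumab during the DLT observation period", stands alone, and the parenthesis again follows the 21-day period.

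Protocol section 2.2 gives the consequence of failing any condition: "All subjects that are not DLT-evaluable will be replaced for the purpose of establishing MTD". It defines the MTD as the highest APX005M dose with nivolumab "for which <33% of DLT-evaluable subjects experience a DLT". Section 7.3.1 makes establishing the MTD the Phase 1b primary endpoint. SAP section 5.4.3.2 tabulates DLTs in the DLT-evaluable population only, and also lists them for Phase 1b without naming a population.

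For safety, protocol section 7.2 and SAP section 3.2 require receipt of both products, and SAP section 5.4.3 bases the safety analyses on that set. Protocol sections 3.1 and 6.3.1 start enrollment and adverse event collection with any product.

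**The concern.** A DLT can be the reason the planned dose is not completed. If completing the dose is a condition of being counted, a severe acute toxicity can disqualify the subject from the rate meant to measure it. Replacement then puts another subject in that place. The bias runs only toward understating toxicity.

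Each dose level rests on 3 to 6 subjects, so one dropped DLT can reverse the result for that level. At DL 3 the same rate is one of the triggers for evaluating DL 2a. A rate of 2/6 exceeds the 33% limit and 1/6 does not. DL 2a can also be opened by two or more Grade 2 reactions at DL 2 or at the sponsor's discretion.

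**Working it through.** **1. Can the case arise under the protocol's own rules?** Yes, in four steps.
- Section 3.4.1.2, for a Grade 3-4 infusion reaction or cytokine release syndrome, says "stop infusion and treat symptoms following guidance in" Table 3. The Grade 2 instruction mentions a restart; this one does not.
- Section 3.7, Table 4, in the row "APX005M infusion reaction/cytokine release syndrome", discontinues both products at Grade 4.
- Section 3.5 makes Grade 4 non-hematologic, non-laboratory toxicity and Grade 5 toxicity DLTs.
- The subject has then not received the entire planned dose, fails sections 7.2 and 3.3, and is replaced under section 2.2.

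Infusions that are interrupted, restarted and completed (sections 3.3.1 and 3.3.2) are unaffected. So are DLTs that begin after the infusion ends.

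**2. The plan's own rule.** Escalation continues at 0/3 = 0% or 1/6 = 16.7%, both below 33%. A result of 1/3 leads to expansion, and 2/6 = 33.3% is not below 33%. The planned total of about 18 is 3 + 3 + 6 + 6. The rule is internally consistent.

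**3. One dropped subject.** If one of two DLTs in six ended the infusion and the replacement has no DLT, 2/6 becomes 1/6 and the level passes. In the same way 1/3 (expand) becomes 0/3 (escalate). This step needs no assumption about how often it happens.

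**4. Effect on the chance of passing a level.** Let p be the true DLT rate and s the share of DLTs that permanently end the infusion. Neither is in the documents. I take p = 33% (the MTD limit) and p = 1/6 (the single-agent figure at 0.6 and 1 mg/kg, protocol section 2.2.2), with s = 5%, 10% and 25%.

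Rule applied mechanically:
- Apparent rate q = p(1 − s)/(1 − ps)
- P(pass) = (1 − q)³ + 3q(1 − q)⁵

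For p = 0.33 and s = 0.10, q = 0.297/0.967 = 0.307 and P(pass) = 0.333 + 0.147 = 0.480.

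Section 2.2 also suspends enrollment pending review after two Grade 4 reactions. If that always blocks the level after a second dropped subject, then with d = ps:
- P(pass) = (1 − p)³(1 + 3d) + 3p(1 − s)(1 − p)⁵(1 + 6d)

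For the same inputs, d = 0.033 and P(pass) = 0.331 + 0.144 = 0.475.

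The chance that at least one DLT is dropped among six treated subjects is 1 − (1 − d)⁶.

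| p | s | P(pass), mechanical | P(pass), with suspension | At least one DLT dropped in 6 |
|---|---|---|---|---|
| 33% | 0 | 43.4% | 43.4% | 0% |
| 33% | 5% | 45.6% | 45.5% | 9.5% |
| 33% | 10% | 48.0% | 47.5% | 18.2% |
| 33% | 25% | 55.7% | 52.5% | 40.3% |
| 1/6 | 0 | 78.0% | 78.0% | 0% |
| 1/6 | 5% | 79.4% | 79.4% | 4.9% |
| 1/6 | 10% | 80.9% | 80.7% | 9.6% |
| 1/6 | 25% | 85.2% | 83.9% | 22.5% |

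At p = 1/6 passing is the right decision, so the rise there does no harm to the escalation decision. The effect vanishes as p or s goes to zero.

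**5. Safety population.** Nivolumab is infused first (section 3.1), and Table 4 discontinues both products after a Grade 4 nivolumab reaction. If that happens in Cycle 1, the subject is enrolled and has adverse events collected and listed, but appears in no safety summary table. A Grade 3 nivolumab reaction differs: Table 4 resumes APX005M alone later, so that subject can still enter the set.

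**The case against.** The strongest reply is that the parenthesis shows the intent: keep subjects lost to toxicity and remove those lost for other reasons. A sensible DLT review would probably count a Grade 4 reaction that ended an infusion. In the first-in-human study a Grade 4 cytokine release syndrome was counted in a DLT-evaluable subject (protocol section 1.2.3), although the text does not say whether that infusion was completed. The intent is plausible, but the wording does not deliver it. In both documents the parenthesis explains the follow-up condition and leaves the dose condition unqualified.

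The size is also open to challenge, and much of that stands:
- Section 2.2.2 reports only Grade 2 or lower single-agent reactions at the doses proposed here. The 1/6 figure comes from doses 2 to 3.3 times the highest level in this study (0.6/0.3 and 1/0.3). The combination rate is not given.
- Many DLT criteria are defined by duration and could not end an infusion. Reaction symptoms may appear up to 48 hours after dosing, against a 60-minute APX005M infusion.
- Opening a new level depends on the totality of the data. One Grade 5 suspected adverse reaction suspends enrollment by itself, which the calculation above does not model.
- The event remains in the DLT and adverse event listings, and the RP2D weighs all adverse events (protocol section 7.4.2, SAP section 4.3.1).

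Finally, SAP section 7 says Phase 1b was reported under SAP version 1.0, whose definition is not available here. The effect on the reported MTD is therefore unknown. These points limit the harm and make the probabilities illustrative. None of them returns the subject to the DLT rate or the MTD.

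**Conclusion.** The definition is wrong as written in both documents. Followed literally, it removes an infusion-ending DLT from the Phase 1b primary endpoint. The group is small: mainly Grade 4-5 events that begin during the first infusion and permanently end it.

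A single case is enough to move a level from failing to passing. On average, at an assumed true DLT rate of 33%, the chance of passing rises by about 2 to 12 percentage points for assumed shares of 5% to 25%, or about 2 to 9 points if the suspension rule always blocks a second case. These may be too high for the doses studied. The direct harm is to the reported DLT rate and MTD rather than to the Phase 2 dose. Whether any subject was affected cannot be told from the documents.

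The safety-population gap is real but secondary. The number of nivolumab-only subjects is unknown and probably small, and the disposition table in SAP section 5.2 would show the difference in counts.

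**What to change.** 1. In protocol section 7.2 and SAP section 3.3, state that any eligible Phase 1b subject who started both products and had an event meeting the section 3.5 definition is DLT-evaluable, whatever dose was completed. Apply the full-dose condition, the 21-day condition and replacement only to subjects without a DLT. Section 3.5 already concerns events attributed to the combination and following administration of both products, so a reaction before any APX005M is not drawn in.
2. Compare the Phase 1b DLT listing with the DLT-evaluable set, and check dosing and replacement records for anyone excluded after an incomplete Cycle 1 dose. If one is found, restate the DLT rate and MTD table. If none is found, say so in the report.
3. Define the safety population in protocol section 7.2 and SAP section 3.2 as all subjects who received any investigational product, in line with protocol sections 3.1 and 6.3.1, and identify nivolumab-only subjects as such.

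The cost is wording in three definitions and one record check. DLT and MTD tables are re-run only if an excluded subject is found, and safety tables change only if there are nivolumab-only subjects. No new data or patients are needed, and no dose or clinical rule changes.
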